## 1. TIME SCHEDULE

Visit number (a)		#1	#3
Period	Screening		Planned treatment
Visit	Screening	Baseline / Randomization (c)	On-site visit
Day	1-7 days (b) prior to randomization	0	90
Window {day[s]}			± 15 d
Study assessments			
Informed consent (IC) (d)	(X)		
Demographics (e)	(X)		
Medical history	(X)		
Functional NYHA class	(X)		X
Prior medication	(X)		
TAVR assessment	(X)		
Inclusion / exclusion criteria	(X)	(X)	
Concomittant medication		(X)	(X)
Physical exam		(X)	(X)
Vital signs (f)		(X)	(X)
Echocardiogram (TTE or TEE) (g)	(X)		X
12-lead ECG		(X)	(X)
4D-computed tomography			X
Study medication			
Prescribing/dispensing assigned therapy		(X) (h)	(X)
NOAF assessment and adjustment of treatment (i)		(X)	(X)
(Serious) adverse events (j)	(X)	(X)	(X)
Laboratory assessments (local labs)			
Hematology (k)	(X)		
Liver tests (l)	(X)		
Renal function (m)	(X)		

(X) Items assessed in the main GALILEO study

**X** Items assessed in the GALILEO-4D substudy only

(a) Visit number #2 at 30 days after randomization is only mandatory in the main GALILEO trial.

(b) Consenting subjects must be randomized within 1-7 days post-TAVR and before hospital discharge.

(c) Once randomized, a subject has entered the study and all randomized subjects will be followed for this substudy until the 4DCT-scan has been performed, even if they did not take assigned study medication or prematurely discontinued study medication. In case of early permanent discontinuation of study medication, all relevant information must be captured in the eCRF as soon as possible after stopping the assigned study medication. The timing of the on-site visit must be kept unchanged.

- (d) A separate informed consent form will need to be signed for the GALILEO-4D substudy.
- (e) Demographics: year of birth, sex and race/ethnicity, if allowed per local regulations.
- (f) Vital signs: blood pressure, heart rate, weight, and height. Note that height only needs to be determined at screening.
- (g) The mean transaortic valve pressure gradient should be determined from either routine transthoracic echocardiogram (TTE) or transesophageal echocardiogram (TEE) recordings before discharge and at  $90 \pm 15$  days after randomization.
- (h) The first study drug administration.
- (i) In case of NOAF after randomization, subjects in: (a) the rivaroxaban-based treatment strategy will be switched to rivaroxaban 15 or 20 mg once-daily, based on kidney function. eGFR will be used as reported in lab printouts or calculated from serum creatinine levels using the MDRD formula. Subjects with moderate renal impairment and  $eGFR < 50$  and  $\geq 30$  mL/min/1.73 m^2 will receive an adjusted dose of rivaroxaban of 15 mg once-daily. Both of these doses must be taken with food. (b) Subjects in the antiplatelet-based treatment strategy will switch to vitamin K antagonist after INR assessment (INR target 2-3).
- (j) Only serious adverse events (SAE) and adverse events (AE) that lead to permanent discontinuation of the assigned study medication are to be reported. The investigator must report immediately (within 24 hours of the investigator's awareness) all (serious) adverse events. (S)AE reporting will be done via the main GALILEO study.
- (k) Hematology tests include hemoglobin, platelet count and white cell count.
- (l) Liver tests include AST/ALT, total bilirubin and its components, and alkaline phosphatase
- (m) Renal function will be estimated by creatinine clearance (Cr-Cl; MDRD formula using serum creatinine levels).

## **2. BACKGROUND**

Transcatheter aortic valve replacement (TAVR) has become an established therapeutic option for patients with symptomatic, severe aortic valve stenosis, who are ineligible or at high risk for conventional surgical aortic valve replacement (SAVR). Results from the NOTION (Nordic Aortic Valve Intervention Trial) randomized clinical trial showed that TAVR may also be a viable option for patients with a lower risk profile.

Very recently, Makkar et al. (2015) reported that leaflet thickening and reduced leaflet motion is not uncommon after both TAVR and SAVR – with an incidence of ~ 20%. Although reduced leaflet motion did not result in higher transvalvular gradients, the authors emphasized that this phenomenon should be further investigated for its effect on clinical outcomes (e.g. stroke) and valve durability. As this valve leaflet thickening and reduced motion could be reversed by oral anticoagulant (OAC) treatment and was not observed in patients on chronic OAC therapy, the authors hypothesized that this phenomenon could be related to possible leaflet thrombosis or a “thrombotic film” on the leaflets.

In the most recent ESC guidelines, the need for a 3-month period of postoperative OAC therapy has been challenged in patients with aortic bioprostheses (class IIb, level of evidence C), with the use of low-dose aspirin now favoured as an alternative. Although the rates of thrombo-embolic events among patients given OAC after surgical bioprosthetic aortic valve implantation appear to be lower than the event rates among patients given aspirin alone, OAC treatment is associated with more bleeding. With the limited evidence to date based primarily on observational studies, the trade-off between reduced thromboembolic events with OAC and increased bleeding remains uncertain.

Currently, treatment of TAVR patients with dual anti-platelet therapy (DAPT; aspirin and clopidogrel) for 3-6 months is widely accepted and recommended – however, this recommendation is not based on hard evidence and the usefulness of DAPT is questioned. Two small studies revealed that the risk for cardiovascular events was not reduced, while the risk for bleeding increased in the DAPT group compared to single antiplatelet therapy. However, antiplatelet-based therapy alone might not be the optimal treatment for TAVR patients.

[figure not shown]
As to date, the optimal therapy for TAVR patients is not known and only based on consensus, there is an unmet need to identify the best medical treatment in patients undergoing TAVR. As novel oral anti-coagulants (NOACs) such as rivaroxaban may reduce the risk for TAVR-related thrombotic events, without increasing the bleeding risk, this study aims to evaluate whether a rivaroxaban-based strategy, following successful TAVR, compared to an antiplatelet-based strategy, is superior in reducing subclinical valve leaflet thickening and motion abnormalities – as detected by four-dimensional, volume-rendered computed tomography (4DCT).

## **3. PURPOSE**

The purpose of this project is to evaluate whether a rivaroxaban-based strategy, following successful TAVR, compared to an antiplatelet-based strategy, is superior in reducing subclinical valve leaflet thickening and motion abnormalities – as evaluated by 4DCT imaging at three months following TAVR.

[figure not shown]
#### 4. STUDY DESIGN

The GALILEO-4D trial will be conducted as a substudy of the multicenter, open-label, randomized, event-driven, active-controlled GALILEO trial. Patients will be 1:1 randomized to an antiplatelet-based strategy vs. rivaroxaban-based strategy – the randomization will adopt the same 1:1 randomization of the main GALILEO trial. In total, 300 patients will be randomized in the GALILEO-4D trial.

The 4DCT-scan should be performed 90days ± 15 days after randomization. The 4DCT-scan should preferentially be performed at the same day of Visit #3 or some days before Visit#3, but should – if possible – NOT be performed after Visit #3.

#### Study design of the GALILEO trial:

Successful transcatheter aortic valve replacement (TAVR) as defined in the main GALILEO study protocol.

R, randomization; ASA, acetylsalicylic acid; OD, once-daily.

## 5. STUDY POPULATION

### 5.1. Inclusion & exclusion criteria

#### ➤ Inclusion criteria

1. Patient included in the randomized GALILEO trial
2. Written informed consent

#### ➤ Exclusion criteria

1. Severe renal insufficiency (eGFR < 30 ml/min/1.73 m^2) or on dialysis, or post-TAVR unresolved acute kidney injury with renal dysfunction ≥ stage 2
2. Iodinate contrast media allergy or other conditions that prohibit CT imaging (i.e. multiple myeloma, etc.)

## 6. STUDY PROCEDURES

[figure not shown]
### 6.1. Patient information

[figure not shown]
The patient is informed orally and in writing by an investigator about the GALILEO-4D substudy and written informed consent is obtained before study inclusion. Patients will have to give written informed consent for the GALILEO and GALILEO-4D substudy before study entry, preferably in parallel. The patient will also receive a copy of the patient information and, if requested, of the informed consent.

### 6.2. Randomization

All criteria of the GALILEO-4D trial have to be fulfilled in order to make a patient suitable for randomization in the GALILEO-4D trial. In order to obtain 1:1 randomization in the GALILEO and GALILEO-4D trial, a stratified randomization will be foreseen for those patients included in both studies.

### 6.3. Antithrombotic/anticoagulant treatment

[figure not shown]
[figure not shown]

**Additional information**

- The route of administration of all medication is oral.
- Clopidogrel 75 mg once-daily and ASA 75-100 mg once-daily are to be continued unchanged, or to be started at the time of randomization if not already being taken. In subjects that are clopidogrel naïve at randomization, a loading dose of at least 300 mg clopidogrel should be administered.
- The first dose of rivaroxaban (10mg once-daily) is given either immediately after randomization or within 1-3 days after the last intake of clopidogrel. Rivaroxaban 10 mg once-daily can be taken with or without food; rivaroxaban 20 mg once-daily should always be taken with food. Rivaroxaban is continued until the end-of-treatment period visit of the main GALILEO trial.

➤ **IN THE EVENT OF NEW-ONSET ATRIAL FIBRILLATION (NOAF):**

### **Additional information**

- In the event of NOAF, the antiplatelet-based strategy will be stopped and a vitamin K antagonist (VKA) with a target INR 2-3 started. ASA 75-100 mg once-daily is to be continued in combination with VKA until 90 days after randomization.
- In the event of NOAF, the dose of rivaroxaban is switched from 10 mg once-daily to 20 or 15 mg once-daily – depending on renal function – for those patients in the rivaroxaban group. Rivaroxaban 20 and 15 mg once-daily should be taken with food. ASA 75-100 mg once-daily is to be continued until 90 days after randomization.

In order to preserve the 1:1 randomization in the main GALILEO trial and avoid excessive and unfounded 'cross-over' from the antiplatelet group to the rivaroxaban group, results of the 4DCT-scan will be kept blinded for the treating physician and patient until the end of the main GALILEO study.

Only in case of a clinical overt ischemic stroke or non-CNS systemic embolism within three months after randomization, an additional cardiac 4DCT-scan within 8 days of this thrombo-embolic event could be considered. The result of this additional cardiac 4DCT-scan could be made available to the treating physician.

### **6.4. Adverse event reporting**

Adverse Event (AE) reporting will be done via the main GALILEO trial as described in the main GALILEO protocol. As the GALILEO-4D study will be a diagnostic sub-study (involving only a single 4DCT-scan and transthoracic echocardiography), no treatment related Serious Adverse Event (SAE)-reporting should be anticipated.

## **7. STUDY ENDPOINTS**

All endpoints will be assessed at three months after TAVR.

### **7.1. Primary endpoint**

- The rate of patients with at least one prosthetic leaflet with > 50% motion reduction as assessed by cardiac 4DCT-scan (total N = 300).

### **7.2. Secondary endpoints**

- The rate of prosthetic leaflets with > 50% motion reduction as assessed by cardiac 4DCT-scan (total N = 900).
- The rate of patients with at least one prosthetic leaflet with thickening as assessed by cardiac 4DCT-scan (total N = 300).

- The rate of prosthetic leaflets with thickening as assessed by cardiac 4DCT-scan (total N = 900).
- Aortic transvalvular mean pressure gradient and effective orifice area (cm^2) as determined by transthoracic echocardiography.
- Functional NYHA class.
- Death, first thromboembolic event (DTE), and safety endpoints (see GALILEO trial) will be assessed in the main GALILEO study and analyzed in the GALILEO-4D substudy with regards to occurrence of the leaflet abnormalities – as exploratory analysis.

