**8. STATISTICAL ANALYSIS**

The primary endpoint of reduced prosthetic leaflet motion is expected to occur in 20% of patients. Equal number of patients are warranted in both treatment groups. A 65% reduction of the GALILEO-4D primary endpoint requires inclusion of 246 patients in order to demonstrate superiority. Taking into account an estimated loss at follow-up of 18% of patients, the total sample size (N) needed to demonstrate superiority will be 300 randomized patients. The primary endpoint will be analysed using an exact Fisher test or a X test, as required.

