**SAMPLE SIZE CALCULATION (Power 0.8, Alpha 0.05)**

- Probability of event in Group A: 0.20
- Probability of event in Group B: 0.07
- Proportion of sample in Group A: 0.50
- Evaluable subjects needed in Group A: 123
- Drop-out: 0.18

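### Do the two leaflet-level secondary endpoints (N = 900) need a stated method for correlation between leaflets of the same patient?

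*Combined protocol and SAP*

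**What the plan says.** Section 4 makes the patient the unit of allocation: "Patients will be 1:1 randomized to an antiplatelet-based strategy vs. rivaroxaban-based strategy", and "In total, 300 patients will be randomized in the GALILEO-4D trial". The primary endpoint in section 7.1 also counts patients: "The rate of patients with at least one prosthetic leaflet with > 50% motion reduction as assessed by cardiac 4DCT-scan (total N = 300".

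Section 7.2 then lists two endpoints whose unit is the leaflet: "The rate of prosthetic leaflets with > 50% motion reduction as assessed by cardiac 4DCT-scan (total N = 900" and "The rate of prosthetic leaflets with thickening as assessed by cardiac 4DCT-scan (total N = 900". Each has a patient-level counterpart read from the same scans: the primary endpoint for motion, and a separate secondary endpoint for thickening.

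Section 8 contains one sentence on testing: "The primary endpoint will be analysed using an exact Fisher test or a" chi-square test. It gives no method for any secondary endpoint, whether leaflet rates, patient-level thickening, mean gradient, orifice area or NYHA class. Correlation between leaflets of one patient is not mentioned anywhere.

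**The concern.** The three leaflets of a prosthesis share the patient, the valve, the assigned drug and the scan. If thickening or reduced motion tends to affect several leaflets of a valve together, 900 leaflets carry less information than 900 independent observations. The only tests the plan names, Fisher and chi-square, assume independent units. Carried over to leaflets, they would give standard errors that are too small under positive correlation, and a chance imbalance between patients could then be reported as a leaflet-level effect of rivaroxaban. Printing N = 900 in the same list as N = 300 invites that reading.

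**Working it through.** **1. The plan's own figure.** Inputs from section 8: event rates 0.20 and 0.07, alpha 0.05, power 0.80, drop-out 0.18. With mean rate 0.135 and a two-sided test,

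n0 = [1.960 x sqrt(2 x 0.135 x 0.865) + 0.842 x sqrt(0.20 x 0.80 + 0.07 x 0.93)]^2 / 0.13^2 = 107.3.

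The continuity correction gives (107.3/4) x [1 + sqrt(1 + 4/(107.3 x 0.13))]^2 = 122.2, rounded up to 123. This agrees with "Evaluable subjects needed in Group A: 123". Then 2 x 123 = 246, and 246/(1 - 0.18) = 300. All of this counts patients, so leaflet correlation does not enter.

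**2. What 900 stands for.** 900/300 = 3 leaflets per randomised patient. With the plan's own losses, about 3 x 246 = 738 leaflets would be read. The primary endpoint is likewise labelled N = 300 although its test is sized on 246. The N values in section 7 therefore name the unit counted; they are not the sample size of a test.

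**3. Error of an unadjusted leaflet test, by assumed ICC.** With three leaflets per patient the design effect is DE = 1 + 2 x ICC, and the true two-sided error is 2 x [1 - Phi(1.96/sqrt(DE))]. The simulated columns use 123 patients per arm, no true effect, beta-binomial leaflets at rates of 6.75% and 9%, and 40,000 replicates.

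| Assumed ICC | DE | 1.96/sqrt(DE) | Formula | Chi-square, simulated | Fisher, simulated |
|---|---|---|---|---|---|
| 0.1 | 1.2 | 1.789 | 7.4% | 7.0-7.4% | 5.4-5.8% |
| 0.3 | 1.6 | 1.550 | 12.1% | 12.0-12.2% | 9.7-10.0% |
| 0.5 | 2.0 | 1.386 | 16.6% | 16.4-16.5% | 13.7-14.0% |
| 0.7 | 2.4 | 1.265 | 20.6% | 20.3-20.9% | 17.5-18.1% |

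**4. Can the documents fix the ICC?** They cannot, because the number of affected leaflets per affected valve is not given. Take leaflet motion at a patient rate of 13.5%, the mean of 20% and 7%. Let p be the leaflet rate and q the probability that two given leaflets of a valve are both affected. Then ICC = (q - p^2)/[p(1 - p)].

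| Affected valves (assumed) | p | q | ICC | Chi-square | Fisher |
|---|---|---|---|---|---|
| all with one leaflet | 0.0450 | 0 | -0.047 | 3.7% | 2.5% |
| 10% with two, rest one | 0.0495 | 0.0045 | 0.044 | 5.6% | 4.1% |
| 20% with two, rest one | 0.0540 | 0.0090 | 0.119 | 7.7% | 5.7% |
| 50% with two, rest one | 0.0675 | 0.0225 | 0.285 | 11.8% | 9.4% |
| 50% with three, rest one | 0.0900 | 0.0675 | 0.725 | 21.6% | 18.8% |

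Even the sign is open. In the one-or-two case the ICC turns positive when the share f of affected valves with two affected leaflets exceeds the solution of f = rate x (1 + f)^2/3. That is about 5% at a patient rate of 13.5%, and 2.5% and 7.7% at rates of 7% and 20%.

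**5. Is a sound analysis available without a change of design?** Yes. An ordinary cluster-robust comparison of leaflet proportions, with the patient as cluster, had a simulated error of 4.8% to 5.4% across these distributions at patient rates of 7%, 13.5% and 20%. With a small-sample variance and t reference it was 4.5% to 5.2%. No special correction is needed, even with only about 0.07 x 123 = 9 and 0.20 x 123 = 25 affected patients expected in the two arms.

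**6. Does the plan prescribe the faulty test?** It does not. Section 8 ties Fisher and chi-square to the primary endpoint, and alpha and power appear only in that endpoint's sample size calculation. Every inflated error rate above belongs to an analysis that the plan does not propose.

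**The case for a change.** The strongest case for a change is this. Section 7.2 labels only its last item, on death, thromboembolic and safety events, as exploratory. The leaflet rates carry no such label in a trial framed around superiority. An analyst holding two named tests and a denominator of 900 could easily run a chi-square test on leaflets. For the patient-level binary endpoints a borrowed Fisher or chi-square test would be valid; for these two it would not be under positive correlation. The break-even share of valves with two affected leaflets is low, and naming the method in advance would prevent a choice made after the results are seen.

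Part of this stands. The text is silent, the arithmetic is right, and clustering is a feature of the leaflet endpoints alone. But silence on method extends to every secondary endpoint, so it does not single these two out. Wording such as "The rate of patients with at least one prosthetic leaflet with > 50% motion reduction" shows that several affected leaflets in one valve are possible, not how often they occur. The larger error rates need an ICC of 0.5 to 0.7, for which the documents offer no support.

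**Conclusion.** The concern describes missing detail, not a wrong rule. Following the plan as written produces no invalid result, because it neither calls for a test on leaflets nor treats them as independent. Analysts can report the leaflet rates descriptively, or compare them with the patient as cluster, without departing from the text.

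The conditional size is about 7% true error at an ICC of 0.1 and 17% at 0.5 for chi-square, somewhat less for Fisher, and below 5% if affected valves have a single affected leaflet. All of these rest on assumed correlations, 123 evaluable patients per arm and all three leaflets read.

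Even if the unadjusted test were used, a reader could set each leaflet result against its patient-level counterpart from the same scans. The primary comparison and the sample size would stand. No change to the plan is called for.

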**Definitions:**

- Leaflet thickening: Hypoattenuating leaflet thickening *or* focal hypoattenuating abnormality attached to the prosthetic leaflet *or* diffuse thickening of the prosthetic valve leaflet identifiable on at least two reconstructed planes (typically double-oblique axial and multiplanar reformatted reconstructions).
- Reduced motion: Reduced systolic leaflet excursion is classified as: (I) normal, (II) mildly reduced (<50%), (III) moderate to severely reduced (>50%), and (IV) immobile. Reduced systolic leaflet excursion is considered significant when it is > 50% or immobile. Quantitative assessment of leaflet motion is performed with a blood pool inversion volume rendered cine reconstruction throughout the cardiac cycle evaluating the bioprosthetic leaflets.

The 4DCT CoreLab evaluation will be performed at Rigshospitalet, Copenhagen (Denmark) under supervision of [name]. [name] and at St. Paul's Hospital, Vancouver, BC (Canada) under supervision of [name]. The readers of the 4DCT-scan will be blinded from the treatment arm.

**8. STATISTICAL ANALYSIS**

The primary endpoint of reduced prosthetic leaflet motion is expected to occur in 20% of patients. Equal number of patients are warranted in both treatment groups. A 65% reduction of the GALILEO-4D primary endpoint requires inclusion of 246 patients in order to demonstrate superiority. Taking into account an estimated loss at follow-up of 18% of patients, the total sample size (N) needed to demonstrate superiority will be 300 randomized patients. The primary endpoint will be analysed using an exact Fisher test or a X test, as required.

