**N = 300**

*Estimation of drop-out rate:*

- A 10% loss at follow-up or death at 3 months is expected in this elderly patient population.
- In approx. 8% of cases, an inconclusive cardiac 4DCT can be expected.

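### Does section 8 need an analysis-set statement and a larger sample because control patients with new-onset AF move to VKA before the scan?

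*Combined protocol and SAP*

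**What the plan says.** Section 8 plans for event probabilities of 0.20 and 0.07 with power 0.8 and alpha 0.05, and gives "Evaluable subjects needed in Group A: 123". It then allows for "an estimated loss at follow-up of 18% of patients, the total sample size (N) needed to demonstrate superiority will be 300 randomized patients". Two items explain the 18%: "A 10% loss at follow-up or death at 3 months is expected in this elderly patient population" and "In approx. 8% of cases, an inconclusive cardiac 4DCT can be expected". The primary test is Fisher's exact or chi-square. Neither section 8 nor any other section names an analysis set.

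Two places direct a change of treatment in control patients who develop NOAF. Section 6.3 says that "the antiplatelet-based strategy will be stopped and a vitamin K antagonist (VKA) with a target INR 2-3 started". Note (i) to the time schedule in section 1 says "Subjects in the antiplatelet-based treatment strategy will switch to vitamin K antagonist after INR assessment". Section 2 reports that the leaflet finding "could be reversed by oral anticoagulant (OAC) treatment and was not observed in patients on chronic OAC therapy". Note (c) in section 1 follows all randomised patients until the scan, "even if they did not take assigned study medication or prematurely discontinued study medication", and leaves the visit timing unchanged.

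**The concern.** The switch is written into the protocol, can happen before the scan at 90 ± 15 days, and by the plan's own background could remove the abnormality being counted. Rivaroxaban patients with NOAF stay anticoagulated, so switching for NOAF dilutes mainly the control arm. Patients who stop rivaroxaban would dilute the contrast from the other side.

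Two things seem to be at stake.

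- **Analysis set.** Keeping switched and stopped patients in their assigned arm narrows the difference. Removing them is a post-randomisation exclusion in an open-label trial. With nothing named, the choice might be made after the data are seen.
- **Power.** The 18% is fully used by lost patients and unreadable scans, and 0.20 and 0.07 are applied to all 123 per group. If those rates are not already net of switching, an as-randomised comparison would have less power than planned.

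**Working it through.** **1. The plan's own figure.** Inputs from section 8: p₁ = 0.20, p₂ = 0.07, difference d = 0.13, mean p̄ = 0.135, power 0.80, alpha 0.05. Alpha is taken as two-sided, the reading that reproduces the stated number.

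n₀ = [1.960·√(2·0.135·0.865) + 0.842·√(0.20·0.80 + 0.07·0.93)]² / 0.13² = 107.3

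With continuity correction: n = (n₀/4)·[1 + √(1 + 4/(n₀·d))]² = 122.2, so 123 per group and 246 in all. Then 246/0.82 = 300. All three stated figures reproduce.

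**2. Which analysis set fits these figures.** 300 × (1 − 0.10 − 0.08) = 246 = 2 × 123. This holds only if nobody with a readable scan is removed for switching or stopping. If 5% or 10% of each arm were removed as off treatment, 123 would become about 117 or 111 per arm. The plan gives neither number. Together with note (c), the arithmetic describes all readable scans, compared by assigned arm.

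**3. Possible dilution.** The documents give no rate of NOAF or of stopping, so 5% to 15% switched is an assumed range. Suppose a fraction r of controls switches and takes on the full 7% rate. The control rate is then 0.20 − 0.13r. Exact power at 123 per arm (sum over two binomials, two-sided p < 0.05):

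| Controls switched | Control rate | Fisher | Chi-square |
|---|---|---|---|
| 0% | 0.2000 | 81.9% | 86.6% |
| 5% | 0.1935 | 78.2% | 83.6% |
| 10% | 0.1870 | 74.1% | 80.1% |
| 15% | 0.1805 | 69.6% | 76.2% |

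Power falls below 80% at 2.7% switched with Fisher and at 10.2% with chi-square.

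**4. How far this depends on the assumption.**

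- *Half the effect gained by the scan* (control rate 0.20 − 0.065r): Fisher 80.1% and chi-square 85.1% at 5% switched; 78.2% and 83.6% at 10%.
- *No events at all after the switch* (control rate 0.20 − 0.20r): Fisher 76.1%, 69.2% and 61.4% at 5%, 10% and 15%.
- *Rivaroxaban patients also stop and return to the full 20% rate*: at 5% switched and 5% stopped, Fisher 72.1% and chi-square 78.3%; at 10% and 10%, 60.6% and 67.9%.

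**5. Which test is likely.** At the planning rates the expected number of events per arm under the null is 123 × 0.135 = 16.6. The usual small-cell reason for Fisher's test therefore does not arise, and the chi-square column is at least as relevant as the Fisher column.

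**The case for a change.** The best case for a change is that note (c) governs data collection. It makes an as-randomised analysis possible without committing anyone to it. The choice can matter: in 20,000 simulated trials analysed both ways by Fisher's test, 7.3% were significant on treatment but not as randomised at 5% switched and 5% stopped, and 17.1% at 10% and 10%. The reverse occurred in 0.6% and 0.4%. One sentence would settle the matter at almost no cost.

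It is true that no section states the analysis set, and that writing it down would do no harm. But the simulated disagreement is with an on-treatment analysis that no section proposes and that does not fit 123 evaluable per group. Treatment adjustment for NOAF is also a scheduled item for both arms in section 1, so a switched patient can be seen as following the protocol. The wording is mixed here, since section 6.3 speaks of the antiplatelet strategy being stopped.

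On power, the strongest point is that 80% is lost by Fisher's test after only a few switches. That needs the full effect to be gained before the scan, the more conservative test, and planning rates that are not already net. Section 2 leaves the last point open. The roughly 20% incidence comes from a report that also observed patients on chronic anticoagulation, and the documents do not say whether those patients are in the denominator. If the rates are net, the stated power stands.

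**Conclusion.** No change to the plan follows. The missing analysis-set statement is a gap in reporting. Note (c) and the drop-out arithmetic both lead to readable scans compared as randomised, and an analyst would fill it that way.

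The sample size of 123 per group, 246 evaluable and 300 randomised is reproduced and not shown to be wrong. At 10% of controls switched with the full effect gained, power would be 74.1% by Fisher and 80.1% by chi-square. The loss is smaller if the effect is partial, larger if switched patients have no events or if rivaroxaban patients also stop, and absent if 0.20 and 0.07 are already net. All of these rates are assumptions, so they give no basis for changing enrolment. The dilution from NOAF switching also works towards no difference, so it would not create a false claim of superiority.

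One limit remains: the main GALILEO protocol and analysis plan were not available and may already define the analysis set.
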